6.4.2.5. Tafasitamab Dose Administered Over Time

For a given infusion, the tafasitamab administered dose will be calculated as

administered dose over time (mg/h) = actual dose administered (mg)/ total infusion time (hours).

6.4.2.6. Dose Interruption and Skipped Doses

6.4.2.6.1. Tafasitamab

There are 2 scenarios for tafasitamab interruption. Firstly, a participant can skip a visit and thus the administration of tafasitamab at that visit. This is defined as "skipping of tafasitamab administration." Secondly, tafasitamab administration can be interrupted during the infusion, this is defined as "interruption of tafasitamab during infusion." Furthermore, a participant

interrupting tafasitamab infusion can have the following scenarios: either the participant takes the full dose after the infusion interruption or the participant does not take the full dose after the infusion interruption. Participants who interrupted or skipped tafasitamab will be indicated in the "Tafasitamab Dosage Administration" eCRF.

6.4.2.6.2. Lenalidomide

If a participant does not take a dose of LEN, that is, skips a LEN capsule for a day, this is considered as a "dose interrupted." Participants who interrupt LEN will be indicated in the "Lenalidomide Dosage Administration" eCRF. Lenalidomide interruption occurs when a participant stops LEN for example to allow for toxicity resolution before restarting the drug.

6.4.2.7. Completion

6.4.2.7.1. Tafasitamab Cycle Completion

A tafasitamab cycle will be considered complete if the participant was exposed to tafasitamab on all planned days of the cycle.

6.4.2.7.2. Tafasitamab Time Period Completion

A tafasitamab time period will be considered complete if all cycles within the period are complete (eg, completed Cycles 1-12 or eg Cycle 13 onwards).

6.4.2.7.3. Lenalidomide Cycle Completion

A LEN cycle will be considered complete if the mean compliance of the cycle is at least 80%.

6.4.2.7.4. Lenalidomide Treatment Period Completion

The LEN treatment period will be considered complete if all 12 cycles are complete.

6.4.3. Study Drug Compliance

6.4.3.1. Compliance With Tafasitamab Treatment

A participant will be considered compliant with the Protocol if the tafasitamab dose administered is 80% to 120% of the assigned dose. Intraparticipant dose reductions of tafasitamab are not permitted.

Infusion interruptions or skipped infusions due to AEs, COVID-19, or logistical or technical reasons will not be considered as noncompliance.

The following strategy will be used to derive the actual administered dose versus the planned dose to calculate compliance with tafasitamab treatment.

Actual dose administered per infusion will be derived as follows:

- Actual dose (mg/kg) = actual dose administered (mg) / weight (kg)
 - Actual dose administered will be taken from the "Tafasitamab Dosage Administration" eCRF. Weight will be taken from the "Vital Signs" eCRF.
- Skipped doses will result in an administered dose of 0 mg/kg for the particular visit

Planned dose per infusion will be derived as 12, 24, or 30 mg/kg as indicated in the "Tafasitamab Dosage Administration" eCRF.

Compliance per infusion will be derived as

compliance rate per infusion (%) = actual dose / planned dose.

Compliance per cycle will be derived as

compliance rate per cycle (%) = actual dose (considering all infusions taken by the participant in the cycle) / planned dose (considering all infusions planned in the cycle).

6.4.3.2. Compliance With Lenalidomide Treatment

Lenalidomide will be taken for the first 21 days of each cycle, and participants may reach the total daily dose by combining capsules of 2 different dose strengths.

The compliance rate per intake (ie, per each day of Days 1 to 21 in a cycle) will be calculated as compliance rate per intake (%) = dose administered / planned dose.

Dose administered and planned dose can be found in the "Lenalidomide Dosage Administration" eCRF.

Compliance with LEN treatment will be derived and reported per cycle. A participant will be considered compliant with LEN treatment for a particular cycle if the mean compliance rate for a cycle is 80% to 120%. The following will not be considered as noncompliance:

- Participants with a transient treatment interruption (an entire cycle skipped or doses skipped on single days) due to an AE, COVID-19, or logistical or technical reasons (as indicated in the "Lenalidomide Dosage Administration" eCRF).
- Participants undergoing treatment discontinuation who took LEN for fewer than 21 days.
- Reduction of the planned dose (eg, due to an AE).

6.4.4. Summaries

6.4.4.1. Dose Reduction of Lenalidomide

The following will be summarized for LEN dose reductions in the SAF, PAS, and FAS:

- Number (%) of participants with any dose reduction.
- Number (%) of participants with a reduction to a minimum of 20, 15, 10, or 5 mg before completion of Cycle 12.
- Number (%) of participants who had no reduction at all or only a reduction to 20 mg (but not lower).

6.4.4.2. Over-Infusion Rate of Tafasitamab

The following will be summarized for tafasitamab in the SAF, PAS, and FAS:

- Number (%) of participants who had at least 1 infusion rate at a given visit greater than the standard infusion rate
- For each cycle, number (%) of participants who had at least 1 infusion rate among visits in a cycle greater than the standard infusion rate

6.4.4.3. Tafasitamab Dose Administered Over Time

Tafasitamab dose administered over time by infusion will be summarized for the SAF, PAS, and FAS.

6.4.4.4. Dose Interruption and Skipped Doses

The following will be summarized for the SAF, PAS, and FAS:

- Number (%) of participants who skipped at least 1 tafasitamab dose
- Number (%) of participants who skipped tafasitamab by cycle and by number of skipped doses
- Number (%) of participants who interrupted at least 1 tafasitamab infusion
- Number (%) of participants who interrupted tafasitamab by cycle and by number of interruptions
- Number (%) of participants who interrupted at least 1 LEN dose
- Number (%) of participants who interrupted LEN by cycle and by number of interrupted doses

6.4.4.5. Study Treatment Exposure

The following will be summarized for the ENR:

- Number (%) of participants who were treated with study drug, split by:
 - any study drug
 - both study drugs
 - any tafasitamab dose
 - at least 1 dose of tafasitamab 24 or 30 mg/kg

any LEN dose

6.4.4.6. Compliance

6.4.4.6.1. Compliance With Tafasitamab

The compliance rate will be summarized and the number (%) of compliant and noncompliant participants will be reported by visit for the SAF, PAS, and FAS.

For visits in which no infusion was planned (eg, EOT), compliance will not be reported.

A listing of tafasitamab dose administration will be provided for the ENR with inclusion in the SAF, PAS, and FAS noted.

6.4.4.6.2. Compliance With Lenalidomide

The compliance rate will be summarized and the number (%) of compliant and noncompliant participants will be reported by cycle (Cycles 1-21) for the SAF, PAS, and FAS.

A listings of LEN dose administration will be provided for the ENR with inclusion in the SAF, PAS, and FAS noted.

6.5. Prior and Concomitant Medication and Nondrug Therapies

6.5.1. Coding

Prior and concomitant medications and preinfusion medications for tafasitamab will be recorded and coded using the WHO Drug Dictionary and grouped by WHO drug class and WHO drug term. Surgical and medical procedures (nondrug therapies) will be coded using MedDRA and summarized by SOC and PT.

6.5.2. Definitions

6.5.2.1. Preinfusion Medication for Tafasitamab

Preinfusion medication for tafasitamab is defined as medication given prior to tafasitamab infusion to mitigate potential IRRs. Premedication encompasses antipyretics, histamine receptor blockers, glucocorticosteroids, and meperidine.

6.5.2.2. Prior Medication/Nondrug Therapies

If the medication/nondrug therapy start and stop dates are both before the start date of study treatment, the medication/nondrug therapy will be classified as prior medication/nondrug therapy.

6.5.2.3. Concomitant Medication/Nondrug Therapies

If the medication/nondrug therapy start date is after start of study treatment, the medication/nondrug therapy will be considered as concomitant medication/nondrug therapy. If the medication stop date is incomplete, the following algorithm will apply:

- If stop day is missing but month is complete, the medication/nondrug therapy will only be excluded from concomitant medication/nondrug therapy if stop month is before month of treatment start.
- If stop day and month are missing but year is complete, the medication/nondrug therapy will only be excluded from the concomitant medication/nondrug therapy if stop year is before year of treatment start.
- If stop date is completely missing, the medication/nondrug therapy will not be excluded.

6.5.2.4. Prior and Concomitant Medication/Nondrug Therapies

If the medication/nondrug therapy start date is before the start date of study treatment but is ongoing or has a stop date after the start of study treatment, it will be considered as both prior and concomitant medication/nondrug therapy.

6.5.3. Prior Lines of Antilymphoma Therapy

Prior antilymphoma therapies (drug or nondrug) will be summarized for the PAS and FAS as follows:

- Prior antilymphoma medications
 - Number (%) of participants by number of prior therapy lines (as categorical variable)
 - Number (%) of participants with 0, 1, or \geq 2 prior antilymphoma medications
- Prior radiation therapy
 - Number (%) of participants with at least 1 prior antilymphoma radiotherapy
- Prior surgery
 - Number (%) of participants with at least 1 prior antilymphoma surgery/procedure
- Prior ASCT
 - Number (%) of participants with prior ASCT

All data will be listed for the ENR with inclusion in the PAS and FAS noted. Listings for individual antilymphoma-specific treatments will include the following:

- Best overall response and date
- Reason for therapy discontinuation
- Therapy start date
- Therapy end date

- Therapy type
- Medication name
- Number of the particular therapy line

6.5.3.1. Time Since Last Antilymphoma Treatment

The time since last antilymphoma treatment will be calculated as

time since last antilymphoma treatment (months) = (date of first dose of study drug – EOT date for last prior antilymphoma treatment [medication/radiation therapy/surgery] + 1) / 30.4375.

6.5.4. Summaries of Non-Antilymphoma Therapies

The following summary tables will be presented for the PAS and FAS:

- Preinfusion medications for tafasitamab
- Prior non-antilymphoma medications
- Concomitant non-antilymphoma medications
- Prior non-antilymphoma nondrug therapies
- Concomitant non-antilymphoma nondrug therapies

All data will be listed based on the ENR with inclusion in the PAS and FAS noted.

6.5.5. Nonstudy Antilymphoma Treatment

Receipt of NALT on or after the start date of study drug will be provided (based on the "Non-Study Lines of Anti-Lymphoma Treatment," "Non-Study Lines of Anti-Lymphoma Treatment: Drug Treatment," "Non-Study Lines of Anti-Lymphoma Treatment: Radiotherapy Treatment," and "Non-Study Lines of Anti-Lymphoma Treatment: Surgeries/Procedures" eCRFs).

The following will be summarized for the PAS and FAS:

- Number (%) of participants who received NALT prior to permanent discontinuation of tafasitamab: any NALT, drug NALT, radiotherapy NALT, surgery/procedure NALT
- Number (%) of participants who received NALT before a documented radiological progression as per IWG Criteria (Cheson et al 2007): any NALT, drug NALT, radiotherapy NALT, surgery/procedure NALT
- Number (%) of participants who received NALT anytime on or after the start date of study treatment: any NALT, drug NALT, radiotherapy NALT, surgery/procedure NALT

In addition, a summary of drug NALT (by WHO drug class and WHO drug term) received anytime on or after start of study treatment will be presented for the PAS and FAS.

Listings of drug NALT, radiotherapy NALT, and surgery/procedure NALT will be presented for the ENR with inclusion in the PAS and FAS noted. Listings will include NALT received any time on or after the start date of study drug, if prior to permanent discontinuation of tafasitamab and before a documented radiological progression as per IWG Criteria (Cheson et al 2007). Listings will include the following:

- Cohort
- Tafasitamab/LEN start and stop dates
- Date of disease progression as per IWG criteria
- If drug NALT, WHO drug class and WHO drug term
- NALT start and stop dates
- Reason for stopping NALT (only if prior treatment)

7. EFFICACY

Appendix A provides a list of data displays. Sample data displays are included in a separate document.

7.1. General Considerations

Response assessment per INV will be based on the response criteria according to Cheson et al (2007; described in Protocol Section 12.4). The outcome of a tumor response assessment will be documented in the "Disease Response Assessment" eCRF (in the "overall response based on Cheson 2007 criteria" field).

The following efficacy endpoints will be analyzed: ORR, DoR, and PFS. Summaries will be presented by treatment group and overall.

7.2. Efficacy Hypotheses

Not applicable.

7.3. Analysis of the Secondary Efficacy Parameter(s)

7.3.1. Endpoint: Objective Response Rate

The ORR is defined as the proportion of participants with CR or PR as the best response achieved at any time during the study. Only responses of CR or PR that were documented before the initiation of NALT will be considered. The denominator will be the total number of participants included in the analysis set.

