**Table 1: Objectives and Corresponding Endpoints**

Objectives	Endpoints
Primary	

 
To evaluate the safety and tolerability of tafasitamab administered ██████████ in combination with lenalidomide in R/R DLBCL patients
 
To determine a recommended dose for tafasitamab ██████████ administration in combination with lenalidomide in R/R DLBCL patients
 
	Incidence and severity of TEAEs
Secondary	
To evaluate the pharmacokinetic profile of tafasitamab after ██████████ dosing in combination with lenalidomide	Tafasitamab serum concentrations after 3 ( $C_{trough}$ and $C_{max}$ ) and 12 ( $C_{trough}$ ) treatment cycles
To assess anti-tumor activity of tafasitamab after ██████████ dosing in combination with lenalidomide	
 
Best Objective Response Rate (ORR) by investigator assessment up to treatment Cycle 12 based on Cheson et al. (2007)
 
Duration of Response (DoR) by investigator assessment based on Cheson et al. (2007)
 
Progression-Free Survival by investigator assessment based on Cheson et al. (2007)
 

To assess the incidence of anti-drug antibodies to tafasitamab	Number and percentage of patients developing anti-tafasitamab antibodies up to treatment Cycle 12

Abbreviations:  $C_{max}$ =maximum concentration;  $C_{trough}$ =minimum concentration; DLBCL=diffuse large B-cell lymphoma; ██████████; R/R=relapsed/refractory; TEAEs=treatment-emergent adverse events. Each treatment cycle is 28 days.

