From Cycle 4 onwards, blood samples for tafasitamab anti-drug antibodies (ADAs) will be collected pre-dose on D1 of every other cycle until Cycle 12, i.e. Cycle 4, Cycle 6, Cycle 8, Cycle 10, Cycle 12.

Tafasitamab PK sample will be taken pre-dose and 30 min  $\pm$  15 min after the end of tafasitamab infusion.

10aTafasitamab PK samples will be taken pre-dose and 30 min  $\pm$  15 min after the end of tafasitamab infusion on C4D1 and afterwards pre-dose on D1 of every other cycle until Cycle 12, i.e. Cycle 6, Cycle 8, Cycle 10, Cycle 12.

PET-CT or PET-MRI should be performed at screening, at C12D28 ( $\pm$  4 days) and at EOT visit unless disease progression was already radiologically confirmed prior to the EOT visit. If progression/relapse is suspected on the basis of clinical symptoms, PET-CT or PET-MRI should be performed to confirm disease progression. PET/CT or PET-MRI from Cycle 25 onwards should be performed only if deemed necessary, and not more than once per year.

11aCT or MRI should be performed within 4 days prior to C3D1, C5D1, C7D1 and C10D1. From Cycle 13-24 CT or MRI should be performed approximately every 3 months  $\pm$  2 days from the previous scan. The first assessment during this phase will take place 3 months  $\pm$  2 days after C12D28. From Cycle 25 onwards: approximately once every year  $\pm$  2 weeks from the previous scan.

Repeat bone marrow biopsy only in those patients who had known bone marrow involvement at screening to confirm a CR. If repeat bone marrow biopsy is required to confirm CR, the assessment should be done at C3D15  $\pm$  1 day and/or within 15 days after C5D1, C7D1, C10D1 and C12D28. Bone marrow assessment from Cycle 13 to 24 approximately every 3 months  $\pm$  2 weeks from the previous assessment to be performed to confirm a CR only in those patients who had known marrow involvement at screening.

Tafasitamab infusions should be given after pre-medication administration 30–120 minutes prior to starting the infusion. For patients who do not experience any grade 2 or higher IRRs with their first four infusions, pre-medication at subsequent treatments may be omitted according to institutional treatment guidelines.

Regardless of the reason for study treatment discontinuation, patients will have a safety follow-up visit or phone call scheduled 90 days after the last dose of the study treatment.

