## 9.3 Efficacy Assessments

Efficacy will be evaluated in terms of ORR, DoR and PFS. The ORR is defined as the proportion of patients with a best overall response of CR or PR ( $ORR = CR + PR$ ) based on local radiological + clinical evaluations up until disease progression or end of treatment, whichever is earlier.

Disease response assessments will be made according to the revised response criteria based on the guidelines of the IWG reported by Cheson *et al.* (2007) (see [Appendix 4](#): International Working Group Resource Criteria for Malignant Lymphoma. All response assessments made by the local radiology + clinical review will be considered for the efficacy analysis.

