#### ***10.3.2.1 Best ORR Until EOS by Investigator Assessment (Secondary Endpoint)***

The best ORR by investigator assessment is defined as the proportion of patients with CR or PR based on the best response achieved until the end of study. The best ORR along with 95% exact CI (using Clopper-Pearson exact method) will be presented. The number and percentage of patients with CR or PR will be presented.

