2.2. Study Objectives and Endpoints

Table 1 presents the objectives and endpoints.

Table 1: Objectives and Endpoints

 	Endpoints
Primary	
• To evaluate the safety and tolerability of tafasitamab administered in combination with LEN in participants with R/R DLBCL	Incidence and severity of TEAEs
• To determine a recommended dose for tafasitamab administration in combination with LEN in participants with R/R DLBCL	
Secondary	
•	Tafasitamab serum concentrations after 3 (C_{trough} and C_{max}) and 12 (C_{trough}) treatment cycles
To assess antitumor activity of tafasitamab doses in combination with LEN	• Best ORR by INV assessment up to Cycle 12 based on Cheson et al (2007)
•	• DoR by INV assessment based on Cheson et al (2007)
•	• PFS by INV assessment based on Cheson et al (2007)
C	Number and percentage of participants developing anti-tafasitamab antibodies up to Cycle 12

Note: Each treatment cycle is 28 days.

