7.3.1.1. Main Estimand Analysis

The estimand of ORR, with its 5 attributes and the strategies for addressing the defined intercurrent events, is presented in Table 5.

Table 5: Estimand of Objective Response Rate

Estimand Attribute		Definition		
Treatment	Tafasitamab in combination with LEN administered for up to 12 cycles in total, after which participants can continue with tafasitamab as monotherapy.			
Population		All participants with R/R DLBCL as per eligibility criteria who received at least 1 dose of tafasitamab and 1 dose of LEN		
Variable	ORR			
Intercurrent events	Event	Strategy	Rationale (if needed)	
	No postbaseline response assessment or not adequately assessed (eg, NE)	Hypothetical strategy	Participant will be considered as nonresponder	
	Treatment discontinuation due to any reason	Treatment policy	All responses will be considered regardless of treatment discontinuation	
	Death without postbaseline assessment or not adequately assessed (eg, NE)	Hypothetical strategy	Participant will be considered as nonresponder	
	Start of any NALT	While on treatment strategy	Only response prior to the start of any new antilymphoma therapies will be considered	
	Study withdrawal due to any reason during the post-treatment disease follow-up	While on treatment strategy	All responses will be considered up to study withdrawal	
Population-level summary	Percentage and 95% CI us	sing the Clopper-Pearson n	nethod	

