APPENDIX A. PLANNED TABLES, FIGURES, AND LISTINGS

This appendix provides a list of the planned tables, figures, and listings for the Clinical Study Report. Shells are provided in a separate document for tables that are not in the Standard Safety Tables v2.0.

The lists of tables, figures, and listings are to be used as guidelines. Modifications of the lists that do not otherwise affect the nature of the analysis will not warrant an amendment to the SAP.

Tables

Table No.	Title	Population	Standard
Baseline and	d Demographic Characteristics		
1.1.1	Analysis Sets	SPS	X
1.1.1.1	Screening Disposition	SPS	X
1.1.2.1	Summary of Participant Disposition	SPS	X
1.1.2.2	Summary of Participant Disposition by Cycle	ENR	X
1.1.3	Summary of Number of Participants Enrolled by Country and Site	ENR	X
1.1.4.1	Summary of Important Protocol Deviations	ENR	X
1.1.4.2	Summary of Protocol Deviations Related to COVID-19	ENR	X
1.1.5	Summary of Treatment Discontinuation Based on Components of Study Treatment	ENR	
1.1.5.1	Summary of Treatment Discontinuation of Both Tafasitamab and Lenalidomide Before Completing 12 Cycles	ENR	
1.1.5.2	Summary of Participants Who Discontinued Tafasitamab at Cycle 13 or Later	ENR	
1.1.6.x	Summary of Statistics of Enrollment	FAS (.1), SAF (.2)	
1.2.x	Summary of Demographics and Baseline Characteristics	ENR (.1), PAS (.2), SAF (.3), FAS (.4)	X
1.3.1.x	Summary of Baseline Disease Characteristics	PAS (.1), FAS (.2)	X
1.3.2.x	Summary of Bone Marrow Involvement at Screening	PAS (.1), FAS (.2)	
1.4.1.x	Summary of Preinfusion Medications for Tafasitamab	PAS (.1), FAS (.2)	X
1.4.2.x	Summary of Non-Antilymphoma Prior Medications	PAS (.1), FAS (.2)	X
1.4.3.x	Summary of Non-Antilymphoma Concomitant Medications	PAS (.1), FAS (.2)	X
1.4.4.x	Summary of Non-Antilymphoma Prior Nondrug Therapies	PAS (.1), FAS (.2)	
1.4.5.x	Summary of Non-Antilymphoma Concomitant Nondrug Therapies	PAS (.1), FAS (.2)	
1.4.6.x	Summary of Prior Lines of Antilymphoma Treatment	PAS (.1), FAS (.2)	
1.4.7.x	Summary of Nonstudy Antilymphoma Treatment	PAS (.1), FAS (.2)	
1.4.8	Summary of Nonstudy Antilymphoma Treatments: Drug Treatments	PAS	X
1.5.x	Summary of General Medical History and Current Medical Conditions	PAS (.1), FAS (.2)	X
Efficacy			•
2.1	Summary of Objective Response Rate by Investigator Assessment	FAS	
2.1.2	Sensitivity Analysis for Summary of Objective Response Rate by Investigator Assessment	PPS	
2.2.1	Summary of Progression-Free Survival by Investigator Assessment	FAS	

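### Best ORR is listed up to Cycle 12 in the Protocol and SAP objectives tables, but SAP 7.3.1 counts responses at any time and no visible analysis applies the Cycle 12 limit

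*SAP*

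**What the plan says.** The objectives tables agree with each other. Protocol Table 1 (Synopsis) lists best ORR "by investigator assessment up to treatment Cycle 12 based on Cheson" under the 2007 International Working Group criteria, and SAP Table 1 (section 2.2) gives the same Cycle 12 limit.

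The sections that define the calculation do not follow them:

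- **SAP 7.3.1:** "The ORR is defined as the proportion of participants with CR or PR as the best response achieved at any time during the study". The only limit is that the response must be documented before NALT starts.
- **SAP Table 5 (7.3.1.1):** for stopping treatment, "All responses will be considered regardless of treatment discontinuation".
- **Protocol 10.3.2.1:** headed "Best ORR Until EOS by Investigator Assessment (Secondary Endpoint"), so it too claims to be the secondary endpoint, with a window ending at end of study.
- **Protocol 9.3:** "evaluations up until disease progression or end of treatment, whichever is earlier".

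SAP Appendix A plans Table 2.1, "Summary of Objective Response Rate by Investigator Assessment", on the FAS, and Table 2.1.2 as its sensitivity version on the PPS. Neither title names a window.

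**The concern.** One endpoint name covers three different quantities: response by Cycle 12, response by progression or end of treatment, and response at any time before NALT. A programmer working from SAP 7.3.1 would produce the third, and it would be read as the first.

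The Cycle 12 limit has content. The stated objective concerns tafasitamab combined with lenalidomide, and Protocol 7.3.2 allows lenalidomide for at most 12 cycles. Cycle 12 is therefore the end of the planned combination period, and later first responses would arise on tafasitamab alone.

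The discrepancy runs one way, because a longer window can add responders but cannot remove them. It can also turn a best response of PR into CR. That would change the CR/PR split in SAP 7.3.1.2 and the subset used for duration of response among complete responders in SAP 7.3.3.4. In an open-label study, leaving three windows available also allows the choice to be made after the results are known.

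**Working it through.** **Step 1. Windows side by side**

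| Place | Last response that counts |
|---|---|
| Protocol Table 1 | Cycle 12 |
| SAP Table 1 | Cycle 12 |
| Protocol 9.3 | Earlier of progression and end of treatment |
| Protocol 10.3.2.1 | End of study |
| SAP 7.3.1 | Any time in the study, before NALT |
| SAP Table 5 | Before NALT or study withdrawal; stopping treatment is ignored |
| SAP 7.3.1.2, 7.3.1.3, Appendix A Tables 2.1 and 2.1.2 | None stated |

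The one ORR sensitivity analysis (SAP 7.3.1.3) changes the analysis set and not the window. SAP section 12 lists version dates only. Nothing visible reconciles the rows.

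**Step 2. Can the windows give different results?**

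Inputs: 28-day cycles; 30.4375 days per month (SAP 4.3.3); the imaging schedule in footnotes 11 and 11a of Protocol Table 3; final analysis about 3 years after the last enrolment (SAP 3.5.3). The calculation takes the last patient enrolled, still on treatment, with no cycle delays.

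- C12D28 = 12 × 28 = day 336; 336 / 30.4375 = 11.0 months. Time left to month 36: 36 − 11.0 = 25.0 months.
- Scheduled response assessments through C12D28: C3D1, C5D1, C7D1, C10D1 and C12D28 = 5.
- After that: "From Cycle 13-24 CT or MRI should be performed approximately every 3 months". Three months is 91.3 days, giving days 427, 519 and 610. The next would be day 701, past the end of Cycle 24 (24 × 28 = day 672).
- From Cycle 25, scans are about yearly from the previous one: 610 + 365 = day 975, or month 32.
- Added by the open window: 4 scheduled scans, making 9 in all.

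**Step 3. Size per patient**

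The plan gives no ORR figure of its own to reproduce. As a check on the interval method, the L-MIND result in Protocol 3.3.2 was recomputed: 46/80 = 57.5%, Clopper-Pearson 95% CI 45.9 to 68.5, which agrees with the Protocol.

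Assume that all of the approximately 51 planned patients are in the FAS. The figure of about 45 in Protocol 5.2 stands in a largely redacted sentence, so it serves only as a second possible denominator.

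- One late first responder: 1/51 = 1.96 points; 1/45 = 2.22 points.
- Three: 3/51 = 5.88 points; 3/45 = 6.67 points.

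For scale, take a Cycle 12 rate close to L-MIND's, 0.575 × 51 ≈ 29:

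| Late first responders | Any-time ORR | 95% CI |
|---|---|---|
| 0 | 29/51 = 56.9% | 42.2 to 70.7 |
| 1 | 30/51 = 58.8% | 44.2 to 72.4 |
| 3 | 32/51 = 62.7% | 48.1 to 75.9 |

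The counts of one and three are illustrations. The documents give no number of late first responders.

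**The case against.** **The SAP follows the Protocol.** Protocol 10.3.2.1 uses the open window and calls it the secondary endpoint, so the SAP did not invent it. This is true, and the conflict does begin inside the Protocol. But the SAP then follows one Protocol section against another and against its own Table 1, so the contradiction remains whichever section governs.

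**The effect is probably small.** Treatment must stop at progression (Protocol 8.2), and no imaging is scheduled after the end-of-treatment visit. A late first responder would therefore ordinarily have to be on tafasitamab past Cycle 12, unprogressed, free of NALT, and without CR or PR at all five earlier assessments. The 25 months and four scans apply only to that group. For the same reason, the Protocol 9.3 window should rarely differ from the any-time window. This stands, and it limits the likely size.

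**Part of the plan cannot be seen.** Protocol Table 8, SAP section 8 and the table shells are not in the available text, so a Cycle 12 output could exist there. This also stands, and the finding is confined to visible text.

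**The Cycle 12 rate can be recovered.** Listing 2.6.2 gives response by visit. That makes the fix cheap, but no visible output reports the rate.

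**Making Cycle 12 the main analysis is a preference.** The treatment attribute in SAP Table 5 includes monotherapy after Cycle 12, which suits the open window. The sponsor may reasonably choose that window, provided both Table 1s are changed to say so.

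**Conclusion.** The inconsistency is real in the current text, and the SAP as written does not report the endpoint it lists. The reported rate can only equal or exceed the Cycle 12 rate. The excess is 2.0 points per late first responder at n=51 (2.2 at n=45), and it is zero if there are none. Confidence is high for the conflict of wording; the effect on the result is unknown and may be small. The sizes assume that the whole planned sample is in the FAS, and the scan count assumes treatment without cycle delays.

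ORR is descriptive (SAP 3.3), so no test, alpha or power figure is affected. The correction should be made before results are known, but it does not threaten the design.

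**What to change.** 1. Report best ORR through the C12D28 assessment, including its +4-day imaging window and before NALT, as the analysis of the listed endpoint. Use the actual C12D28 assessment date, because cycles can be delayed, and state the cut-off date for patients who never reach that visit.
2. Report best response at any time before NALT as a separately labelled row.
3. Align Protocol 9.3, Protocol 10.3.2.1, SAP 7.3.1 and SAP Table 5. State whether responses after progression or after end of treatment count. If Cycle 12 is the main window, check that the treatment attribute in Table 5 still fits.
4. If the sponsor keeps the until-end-of-study window as the main one, correct both Table 1s and still show the Cycle 12 rate, so that the endpoint listed until now is reported.
5. Name the window in the titles of Tables 2.1 and 2.1.2.

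The cost is one date condition and one extra row from data already collected, plus wording changes in four sections and two table titles. The Cycle 12 rate may come out equal to or slightly below the any-time rate. The cut does not remove unequal follow-up at the primary completion analysis, nor responses on tafasitamab alone in patients who stop lenalidomide early.
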